6.3.3. Exploratory Analysis

6.3.3.1. Time to progression

TTP will be calculated based on BICR assessment review from the first date of receiving study drug until radiographic disease progression.

The rules for censoring TTP are similar to PFS censoring. These are summarized in the table below:

Table 8: Censoring Scheme for TTP

Situation	Date of progression or censoring	Outcome
No baseline or post-baseline tumor assessments	Randomization / Cohort assignment	Censored
Progression documented between scheduled visits	Date of radiological assessment of measured lesions	Progressed
No progression	Date of last radiological assessment of measured lesions	Censored
Treatment discontinuation for reasons other than disease progression by BICR	Date of last radiological assessment of measured lesions	Censored

TTP will be analyzed using Kaplan-Meier methodology (Kaplan & Meier 1958). The median duration of TTP will be presented along with 2-sided 95% CI. If they are calculable, the 25th and 75th percentiles and the 2-sided 95% CIs around the percentiles will be presented. Kaplan-Meier estimates at 3, 6, 9 and 12 months will also be presented. The Kaplan-Meier survival curves will also be presented. For substudy 4 comparison

between cohorts will be made by considering a hazard ratio, with associated 2-sided 95% confidence interval and p-value, from an unadjusted Cox proportional hazards model.

6.3.3.2. Subgroup Analyses

Subgroup analyses (consisting of separate analyses within each subgroup) will be undertaken for all efficacy endpoints considering the following subgroups:

- FGFR1-3 mutation
- Other gene aberration types
- Upper tract urothelial cancer
- Lower tract urothelial cancer
- Stratification factor composite score (0-1 points) – substudy 4 only
- Stratification factor composite score (2-3 points) – substudy 4 only
- Stratification factor: Visceral metastasis – substudy 4 only
- Stratification factor: ECOG PS ≥ 2 – substudy 4 only
- Stratification factor: FGFR inhibitor internal of less than 6 months – substudy 4 only

6.3.3.3. iRECIST (Substudies 3 and 4)

Analyses of ORR, DCR, DOR and PFS will be repeated as outlined above evaluated by BICR using iRECIST criteria ([Seymour 2017](#)).

6.3.3.4. Crossover patients (Substudy 4)

There will be no specific analysis for crossover patients, due to low sample size. Crossover patients will not be included in summary tables/figures and their data will be listed only.

6.3.3.5. Investigator assessed response

In the primary analysis, tumor response will be based upon measurements evaluation by the BICR. However, an initial assessment of tumor response will be made by investigators at site. As an exploratory measure, analyses of BOR, DCR, DOR, PFS will be conducted considering investigator assessment only.

6.4. Safety Analysis (All substudies)

All safety analyses will be performed using the safety/ITT population, apart from in the analysis of DLTs in substudy 2 which will be performed using the MTD population (see Section 5.4). Analyses will be presented by substudy and cohort.

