4.5.3 Replacement of patients

Patients who are non-evaluable for efficacy (see Section 8.2.2) are to be replaced.

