8.3.5 Safety data analysis

Safety will be assessed through summaries of DLTs, AEs, safety laboratory evaluations, physical examinations, and vital signs. All safety analyses will be based on the Safety population. Analyses will be presented by substudy and cohort. The DLTs will be listed and summarized using descriptive statistics.

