5.1. Safety Population/ Intent-to-treat Population

The safety/intent-to-treat (ITT) population consists of all patients with an eligible FGFR1–3 GA who received at least one dose of derazantinib or atezolizumab. Safety data will be summarized according to the treatment actually received.

In the primary safety comparison, patients who crossover to derazantinib-atezolizumab combination are censored at time of crossover (i.e., AEs occurring during treatment with derazantinib-atezolizumab combination are excluded for Cohort 4a patients).

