5.4. Maximum-tolerated Dose (MTD) Population (Substudy 2 only)

The MTD-determining population includes all patients enrolled in the MTD Part of each dose level who meet the following minimum criteria during the DLT period:

- received at least one dose of derazantinib and atezolizumab and has experienced a DLT;
- received $\geq 90\%$ of the derazantinib and atezolizumab dose, respectively, in Cycle 1 and did not experience a DLT, have been observed for ≥ 21 days following the first dose, and have been evaluated for safety.

In the event that Cycle 1 exceeds 21 days, the period for patient's evaluability and DLT assessment will remain at 21 days.

Patients who do not meet these minimum evaluation requirements will be regarded as ineligible for the MTD-determining population. These patients will be included in the safety/ITT population but will be excluded from the calculation of DLT incidence and will be replaced by recruitment of additional patients.

Interim analyses for DLTs may be performed once at least five patients have been enrolled to a particular dose level, full DLT/safety data are available and a patient has not experienced a DLT, or when two DLTs have been observed in any number of patients enrolled in MTD Part of a particular dose level, whichever occurs first. Interim analyses are performed to determine if dose escalation is justified (or dose de-escalation is required) and if derazantinib in combination with atezolizumab is safe and tolerable.

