6.4.2. BLRM analyses for Dose-limiting toxicity (Substudies 3 and 5 only)

Safety interim analyses will be performed once 10 patients have been enrolled and full safety data are available to determine if the revised dosing regimen of 200 mg BID derazantinib either as monotherapy or in combination with atezolizumab is safe and tolerable.

The safety evaluation will comprise updating a three-parameter cumulative BLRM-EWOC design for the incidence of DLTs with monotherapy and combination therapy to strictly manage the risk of excessive toxicity (Neuenschwander 2008). For a derazantinib dose d , let π_d denote the probability of DLT at dose d . If n subjects are evaluated at dose d , then the number of subjects, y , experiencing a DLT is assumed to follow a binomial distribution:

$$y \mid \pi_d \sim \text{Binomial}(n, \pi_d)$$

The relationship between monotherapy and combination derazantinib doses, and DLT probabilities is modelled by the logistic curve;

$$\log(\pi_d/(1 - \pi_d)) = \log(\alpha_i) + \beta \log(d/d^*), \alpha_1, \alpha_2, \beta > 0$$

Doses are rescaled as d/d^* with reference dose $d^* = 600\text{mg/day}$. The model parameters α_1 , α_2 and β have the following interpretation:

- α_1 equals the odds of toxicity with monotherapy at the reference dose d^* .
- α_2 equals the odds of toxicity with combination therapy at the reference dose d^* .
- Doubling the dose results in an increase in odds of toxicity by a factor of 2β .

The model parameters $\log(\alpha_1)$, $\log(\alpha_2)$, $\log(\beta)$ are given a weakly informative multivariate normal prior distribution, following (Neuenschwander 2014), with prior means (-1.386, -1.386, -0.781), prior standard deviations (5.472, 5.472, 0.973), and prior correlations of 0. This prior distribution ensures wide confidence intervals for toxicity probabilities at each dose.

With an acceptable target toxicity range for a dose defined as a probability of toxicity of 10% to <25% and an overdosing range of $\geq 25\%$, the posterior probability of overdosing will be updated over time. Data resulting in a posterior probability of overdosing for a dose in excess of 25% will be determined as unacceptable. This ensures a safe recommended dose is chosen for subsequent testing of anti-tumor efficacy. This process also involves regular dose decision meetings to review the updated cumulative model results as well as safety in individual patients.

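### DLTs in Substudies 3 and 5 are counted over every dosed patient, with no DLT-evaluable set, so early leavers pull borderline results toward tolerable

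*SAP*

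**What the plan says.** SAP 6.4 gives the general rule: "All safety analyses will be performed using the safety/ITT population". The one exception follows: "apart from in the analysis of DLTs in substudy 2 which will be performed using the MTD population". The Bayesian model for DLTs in Substudies 3 and 5 (SAP 6.4.2) sits under that rule. Protocol 8.3.5 is at least as broad: "All safety analyses will be based on the Safety population". Membership of the safety/ITT set requires an eligible aberration and is otherwise open to any patient "who received at least one dose of derazantinib or atezolizumab" (SAP 5.1). It sets no minimum Cycle 1 exposure or observation time.

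SAP 5.4 defines a stricter set but heads it "Maximum-tolerated Dose (MTD) Population (Substudy 2 only)". A patient belongs if a DLT occurred, or if at least 90% of each drug was taken in Cycle 1 with at least 21 days of observation and no DLT. Others are "excluded from the calculation of DLT incidence and will be replaced by recruitment of additional patients". For Substudies 3 and 5 the only replacement rule is in Protocol 4.5.3: "Patients who are non-evaluable for efficacy (see Section 8.2.2) are to be replaced".

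The safety interim is timed as follows: "Safety interim analyses will be performed once 10 patients have been enrolled and full safety data are available" (SAP 6.4.2). A regimen is unacceptable if the posterior probability that its DLT rate is 25% or more exceeds 25%.

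**The concern.** The proportion of patients with DLTs is the primary safety endpoint of the interim in both substudies (Protocol 3.2.1.2), and the posterior overdose probability is the only numerical tolerability criterion. A patient who leaves on, say, day 5 for progression has been observed for a fraction of the 21-day DLT window, yet enters the denominator with the same weight as one who completed it. For a given number of DLTs, this always lowers the estimated rate.

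Two features sharpen the point. Substudy 2 tested 200 and 300 mg/day under the stricter denominator, while Substudies 3 and 5 test 400 mg/day under the looser one. And the model is cumulative, so Substudy 2 data gathered under one denominator rule are combined with new data counted under another. At stake is whether a borderline regimen is judged acceptable at the interim and enrollment resumes.

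**Working it through.** The documents give no operating characteristic for the DLT interim, so there is no stated figure to reproduce. The check applies the stated model to the same DLT count with different denominators.

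**Model (SAP 6.4.2).** logit(π_d) = log(α_i) + β·log(d/600), with i = 1 for monotherapy and i = 2 for combination. Priors are independent normal: log(α_1) and log(α_2) with mean −1.386 and SD 5.472; log(β) with mean −0.781 and SD 0.973. Since log(0.2/0.8) = −1.386, the prior centre is a 20% DLT rate at 600 mg/day.

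**Quantity.** The tested dose is 2 × 200 = 400 mg/day. Overdosing means π_400 ≥ 0.25, that is log(α_i) + β·log(400/600) ≥ log(0.25/0.75), or log(α_i) − 0.405β ≥ −1.099. Its posterior probability was found by grid integration; a Monte Carlo run of 6 million draws agreed within 0.002.

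**History in the documents.** Monotherapy at 400 mg: 0/12 (Protocol 7.1.1.1). Combination: 0/7 at 200 mg and 0/6 at 300 mg (Protocol 1.4.1.2). Protocol 7.1.1.1 also reports DLTs at 250 and 425 mg but gives no counts. Three assumed sets were tried: 1/6 and 1/6; 1/6 and 2/6; 1/3 and 2/3.

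**Results.** Each row takes the highest DLT count that still passes with n = 10. Columns give the posterior overdose probability by number of patients in the denominator.

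| History at 250 and 425 mg | Substudy, DLTs | n = 10 | n = 9 | n = 8 | n = 7 | n = 6 |
|---|---|---|---|---|---|---|
| none entered | 3, 3 DLTs | 0.173 | 0.212 | **0.258** | **0.314** | **0.381** |
| none entered | 5, 4 DLTs | 0.190 | 0.223 | **0.261** | **0.303** | **0.350** |
| 1/6 and 1/6 | 3, 3 DLTs | 0.130 | 0.159 | 0.193 | 0.233 | **0.281** |
| 1/6 and 1/6 | 5, 4 DLTs | 0.153 | 0.177 | 0.203 | 0.232 | **0.264** |
| 1/6 and 2/6 | 3, 3 DLTs | 0.137 | 0.167 | 0.203 | 0.246 | **0.296** |
| 1/6 and 2/6 | 5, 3 DLTs | 0.154 | 0.178 | 0.204 | 0.233 | **0.265** |
| 1/3 and 2/3 | 3, 3 DLTs | 0.134 | 0.163 | 0.198 | 0.240 | **0.289** |
| 1/3 and 2/3 | 5, 2 DLTs | 0.170 | 0.197 | 0.228 | **0.263** | **0.301** |

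Bold exceeds the 0.25 limit. One non-evaluable patient never changes the verdict. Two change it only when the DLTs at 250 and 425 mg are left out. With them in, it takes 3 (one row) or 4. One DLT more than shown already fails at n = 10, and one fewer passes at every n from 6 to 10.

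The crude rates move from 3/8 = 37.5% to 3/10 = 30%, and from 4/8 = 50% to 4/10 = 40%.

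**Exposure of an early leaver.** Protocol 1.4.3.1 gives a half-life of 8 to 10 days. Under simple first-order accumulation (an approximation), the fraction of steady state reached at day t is 1 − 2^(−t/half-life): 29% to 35% at day 5, against 77% to 84% at day 21.

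**The case against.** Four objections deserve weight.

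- **The denominator may already be meant to be evaluable patients.** SAP 6.4.2 takes n as the subjects evaluated at a dose and waits for full safety data, and the schedule of assessments fixes the DLT window at Cycle 1 days 1 to 21. A reader could infer an evaluability condition. But neither term is defined, and the only explicit statement of the analysis set is SAP 6.4, whose single exception is Substudy 2. The inference does not override it.
- **The zero-DLT history is incomplete.** This stands. The model is to take the DLTs at each dose previously explored (Protocol synopsis), and DLTs did occur at 250 and 425 mg. A reader might infer that two early leavers would be enough to pass a regimen that should fail. The documents do not support that: it depends on leaving those DLTs out, and the true counts are not given.
- **The model does not decide alone.** This also stands. The decision is joint, on DLT, AE and PK data and individual patient safety. Under Protocol 7.3.3, interruptions and reductions that are not DLTs still inform benefit-risk. With 10 patients, early departures would be visible.
- **Copying the 90% dose cut is not neutral.** Protocol 6.1.1.5 directs holds for some toxicities, and 7.3.3 calls dose modification not unusual with this class. The cut could drop patients observed for all 21 days without a DLT and push the rate up. This stands against copying it by default, not against having an evaluable set.

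A reader might also call these patients unexposed. That is too strong: all have had at least one dose. They are under-exposed and under-observed.

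**Conclusion.** The gap is real. As written, DLTs in Substudies 3 and 5 are analysed over all dosed patients, with no DLT-evaluable set or DLT replacement rule, although the same SAP supplies both for Substudy 2. For a given DLT count, the direction of the bias is certain: toward tolerable. Its size is modest and confined to borderline counts. Two non-evaluable patients of 10 change the model's verdict under the zero-DLT history alone; 3 to 4 are needed under the three assumed histories that include DLTs at 250 and 425 mg; one never does in any scenario tried. These figures rest on the stated priors, daily dose as the model's dose, and assumed counts at 250 and 425 mg. The documents do not show that the interim would pass an unsafe regimen, because the joint review of AE and PK data remains. The sponsor should correct this, but it does not undermine the design.

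**What to change.** Amend SAP 5.4, 6.4 and 6.4.2 and Protocol 8.3.5 as follows.

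- Define a DLT-evaluable set for Substudies 3 and 5: a DLT in Cycle 1, or completion of the 21-day window with a pre-stated minimum Cycle 1 exposure (derazantinib only in Substudy 5).
- Have the sponsor state how toxicity-related holds count toward that minimum, rather than carry over the 90% cut by default.
- State that the primary safety endpoint and the model's n use this set.
- Run the safety interim on 10 DLT-evaluable patients, replacing those who are not evaluable.
- Keep the safety/ITT DLT summary as supportive.

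The cost is protocol and SAP wording and possibly one or two replacement patients per interim. Those patients still count toward Stage 1 (18 in Substudy 3, 13 in Substudy 5) if evaluable for efficacy.

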6.4.1. Adverse Events

Adverse events will be graded according to the NCI CTCAE Version 5.0, coded using the MedDRA coding system (version 22.0 or later), and displayed in tables and data listings by system organ class (SOC) and preferred term (PT). Dose-limiting toxicities (DLTs) are applicable to substudy 2, substudy 3 and substudy 5 only and are classified as the occurrence of any toxicity during Cycle 1 if judged by the investigator to be possibly or probably related to study drug administration from a pre-specified list in the protocol version 5 for substudies 3 and 5, and protocol version 4 for substudy 2.

Analyses of AEs will be performed for those events that are considered treatment-emergent, where treatment-emergent is defined as any condition that was not present prior to treatment with study medication but appeared following treatment, was present at treatment initiation but worsened during treatment, or was present at treatment initiation but resolved and then reappeared while the individual was on treatment (regardless of the intensity of the AE when the treatment was initiated). A condition present at baseline that worsens after initiation of study treatment will be captured as an AE with the onset date as the date the event worsened. AEs will be reported (considered treatment-emergent) up to the end of the safety follow-up period.

Adverse events are summarized by patient incidence rates; therefore, in any tabulation, a patient contributes only once to the count for a given SOC or PT (i.e., the most related occurrence or the most intense occurrence). Missing relationship will be considered related to study drug.

An overall AE incidence summary table will be produced and will include:

- The number and percentage of patients reporting at least 1 treatment-emergent AE (TEAE)
- The number and percentage of patients reporting at least 1 serious TEAE (SAE)
- The number and percentage of patients reporting at least 1 related TEAE
- The number and percentage of patients reporting at least 1 related serious TEAE (SAE)
- The number and percentage of patients reporting at least 1 AE of Special Interest (AESI)
- The number and percentage of patients reporting at least 1 serious AESI
- The number and percentage of patients reporting at least 1 TEAE with toxicity grade of 3 or higher
- The number and percentage of patients reporting at least 1 related TEAE with toxicity grade of 3 or higher
- The number and percentage of patients reporting at least 1 TEAE classified as a DLT (Substudy 2, 3 and 5)
- The number and percentage of patients reporting a TEAE leading to a dose modification/interruption
- The number and percentage of patients reporting a TEAE leading to permanent discontinuation of study drug
- The number and percentage of patients with a TEAE leading to death

The overall AE incidence summary table described above will also include the number of events reported.

For all event types listed above in the overall AE incidence summary table, tabulations by SOC and PT will also be produced. Related TEAEs with toxicity grade of 3 or higher will also be summarised. These will be presented by SOC and PT, sorted by decreasing frequency.

No formal hypothesis-testing analysis of AE incidence rates will be performed. All AEs occurring on-study will be provided in data listings. By-patient listings also will be provided for the following: SAEs, DLTs (Substudy 2, 3 and 5), AEs leading to permanent discontinuation of study drug, and AEs leading to death.

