5.2.2.8 Safety follow-up (28 days after last dose; \pm 3 days)

All patients will be followed for a minimum of 28 days after the last dose of all study treatment. During the 28-day safety follow-up period, all AEs/SAEs and changes in concomitant medication should be reported.

Patients with unresolved study drug-related AEs (which occurred during the study treatment period or in the 28-day safety follow-up period; see Section 7.2.4 for the definition of a suspected AE) will be followed until, in the opinion of the Investigator, study drug-related toxicities have resolved to baseline, CTCAE grade 1, stabilized, or are deemed to be irreversible.

In addition, at the 28-day safety follow-up visit, the following assessments will be made:

- Physical examination, including weight and vital signs (see Section 5.3.2.1)
- ECOG PS (see Section 5.3.2.2)
- Triplicate 12-lead ECG (Section 5.3.2.4)
- Clinical safety laboratory blood tests (see requirements in Section 5.3.2.5)

- Serum or urine pregnancy testing (to be performed monthly until 150 days after the last administration of study drug) (see Section 5.3.2.7, and Section 7.1.3)
- Blood samples for derazantinib PK, if applicable (See Section 5.3.4.1 for details of applicable patients/ sampling schedule)
- Blood samples atezolizumab and ADA (**Substudy 3 Cohort 4b, and Crossover**; see Section 5.3.4.2 for details of applicable patients/ sampling schedule)

5.2.2.9 *Safety follow-up (90 days after last dose; ± 3 days)*

All patients who receive atezolizumab in **Substudy 3, Cohort 4b, and Crossover** will be followed for a minimum of 90 days after the last dose of all study treatment. During the 90-day safety follow-up period, all AEs/SAEs, changes in concomitant medication, and new anticancer treatment should be reported.

Patients with unresolved study drug-related AEs (which occurred during the study treatment period or in the 90-day safety follow-up period; see Section 7.2.4 for the definition of a suspected AE) will be followed until, in the opinion of the Investigator, study drug related toxicities have resolved to baseline, CTCAE Grade 1, stabilized, or are deemed to be irreversible.

In addition, at the 90-day safety follow-up visit, the following assessments will be made:

- Physical examination (see Section 5.3.2.1)
- ECOG PS (see Section 5.3.2.2)
- Triplicate 12-lead ECG (Section 5.3.2.4)
- Clinical safety laboratory blood tests (see requirements in Section 5.3.2.5)

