7.4.2 Handling of safety data during the pre-treatment period

Any relevant change in, or worsening of, a patient's condition occurring after any informed consent has been provided but prior to the start of first study-drug administration, is to be recorded in the eCRF as pre-dose medical history (see Section 5.3.1.1). However, in this period (between ICF and start of study medication), if an AE/SAE is assessed as related to the study procedure, the AE/SAE is to be reported accordingly in the eCRF as medical history and, in addition, SAE must also be reported to the Sponsor's safety representative, using the same procedures as for an SAE (see Section 7.4.3.2).

7.4.3 Handling of safety data during the treatment period and up to the last scheduled follow-up

From the start of first dosing up to and including the Safety Follow-Up visits 28 and – if applicable – 90 days after last study drug administration, respectively, any change in, or worsening of, a patient's condition must be collected and reported in the eCRF as an AE (see Section 7.4.3.1). Serious adverse events and AESIs must be additionally reported on the SAE/AESI report form (see Section 7.4.3.2).

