7.4.3.1 Adverse event management

7.4.3.1.1 Data collection

All AEs directly observed (physical examination, laboratory test or other assessments), mentioned by the patient, or reported by the patient upon non-directive questioning, must be recorded on the AE pages of the eCRF.

All AEs must be recorded in the English language in the eCRF and should include the following information:

- Term. If possible, a diagnosis should be documented rather than signs and symptoms, using self-explanatory and concise medical terminology. However, if an observed or reported sign or symptom is not considered a component of a specific disease or syndrome by the Investigator, it should be recorded as a separate AE. Progression of disease is considered an efficacy outcome parameter and should not be captured as an AE or SAE, unless its outcome is death.
- Duration (start and end dates).
- Toxicity grade (CTCAE grade; see Section 7.3.1).
- Relationship to the study treatment (causality assessment; see Section 7.3.2).
- Action(s) taken with regards to study drugs (derazantinib and atezolizumab), or any suspected concomitant medication
- Additional treatments given for the event.
- Whether it is an SAE (seriousness assessment; see Section 7.2.2).
- Outcome.

Refer to the eCRF completion guidelines for further details on completing the AE/AESI/SAE in the eCRF.

In addition, the concomitant medications (with indication start and stop (if not ongoing) and Medical history should be updated as needed.

Abnormal laboratory results should not be recorded as an AE unless the abnormal result meets one or more of the following criteria:

- induces clinical signs or symptoms which require therapy or additional diagnostic evaluation
- requires dose modification derazantinib, or discontinuation of study participation
- is considered clinically significant

If a laboratory abnormality meets one of the above criteria, the clinical syndrome associated with laboratory abnormality is to be recorded, as appropriate (e.g., diabetes mellitus instead of hyperglycemia).

AEs must also be reported in the source document with at least the nature of the event, the start and end date, the relationship to the study drugs (derazantinib and/or atezolizumab), treatment (if applicable), and outcome (in initial or follow up report).

7.4.3.1.2 *Follow-up*

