7.4.4 Handling of post-study safety data

After the Safety Follow-up visit(s), only study drug related SAEs and AESIs (see Section 7.2.6) should be collected and reported; however, these events should not be captured in the eCRF system.

New study drug related SAEs and AESIs that occur after the 28-day Safety Follow-up visit (or 90-day Safety Follow-up visit for atezolizumab-treated patients) will be followed until they have, in opinion of the Investigator, resolved to baseline, CTCAE grade 1, stabilized, or are deemed to be irreversible (including death).and if the patient withdraws their consent.

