Abbreviations: ADA: anti-drug antibodies; AE: adverse event; C: cycle; D: day; ECG: electrocardiogram; ECOG PS: Eastern Cooperative Oncology Group Performance Status; PK: pharmacokinetics; PRO: patient reported outcome; PSV: Pre-screening visit; S[n]: Substudy [number]; SIAP: safety interim analysis patients; SV: Screening visit.

	PSV	SV	Cycle 1			Cycle 2+			End of Treatment	Safety Follow-Up		Overall Survival Follow-Up
Assessment window	-	D -28 to D -1	D1	D8 (±3)	D15 (±3)	D1 (+3) ¹	D8 ² (±3)	D15 ² (±3)	≤ 7 days after last dose	28 days after last dose (±3)	90 days after last dose (±3) ³	At least every 3 months from date of last dose (±14)
Substudy applicability	S1/S3/S5	All	All	SIAP S3/S5	All	All	SIAP S3/S5	SIAP S3/S5	All	All	S3/S4	All

For footnotes, see next page.

- Deviations from the visit schedule by +3 days are permitted for reasons other than toxicity, e.g., for administrative reasons or to accommodate travel logistics. If a patient visit deviates from the permitted protocol window, the next visit must be performed at the correct timing based on the date of C1D1.
- Only applicable to Cycle 2.
- Applicable to all patients who received atezolizumab as part of their study treatment.
- Applicable to **Substudies 1, 3 and 5** only).
- Screening procedures comprise assessment of eligibility criteria; medical history of cancer diagnosis and treatment; demographics, medical history, prior medications, baseline medical conditions, including weight and height; Bellmunt score assessment, tuberculosis blood test (e.g., interferon-γ release assay) if clinically indicated to rule out clinical suspicion of active tuberculosis; serology for human immunodeficiency virus, hepatitis B, and hepatitis C.
- Patients will have complete ophthalmological examination, including optical coherence tomography (OCT), during Screening, the first four cycles (i.e., Day 1 [±7d] of Cycles 2–5) and the End of Treatment visit. A complete ophthalmological examination is to be repeated if new ocular symptoms occur or vision is impaired.

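### Substudy 4 safety tables count adverse events to 28 days after last dose in Cohort 4a but to 90 days in Cohort 4b, so their side-by-side incidences are not like for like

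*SAP*

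**What the plan says.** The SAP gives no number of days for the treatment-emergent window. Section 6.4.1 ties it to follow-up: "AEs will be reported (considered treatment-emergent) up to the end of the safety follow-up period". The length of follow-up depends on the drugs received:

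- Protocol 5.2.2.8: "All patients will be followed for a minimum of 28 days after the last dose of all study treatment".
- Protocol 5.2.2.9, for atezolizumab recipients in Substudy 3, Cohort 4b and Crossover: "will be followed for a minimum of 90 days after the last dose of all study treatment".
- SAP Table 1, footnote 3, on the 90-day visit: "Applicable to all patients who received atezolizumab as part of their study treatment".
- Protocol 7.4.3 collects AEs in the eCRF "up to and including the Safety Follow-Up visits 28 and – if applicable – 90 days after last study drug administration".

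Protocol 4.5.1 draws the same 28/90 line. Protocol 3.1.5 does not fit: it lists both visits without saying that the second is restricted.

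SAP 6.4.1 summarises AEs by patient incidence, and SAP 6.4 presents them by substudy and cohort. SAP 5.1 adds a rule specific to Cohort 4a: "In the primary safety comparison, patients who crossover to derazantinib-atezolizumab combination are censored at time of crossover". Protocol 8.2.1 says the same. SAP 3.3 describes the cohorts as randomised 1:1 but non-comparative, and SAP 6.4.1 rules out hypothesis tests of AE incidence.

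**The concern.** Randomisation makes Cohorts 4a and 4b the one place in this study where a reader can judge what atezolizumab adds to the toxicity of derazantinib. If one column counts 62 more days after treatment than the other, part of any difference comes from the calendar and not from the drug.

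The extra days are not neutral. SAP 6.4.1 does not stop counting when a new anti-cancer treatment starts, so toxicity of the next therapy can enter the 4b tables. Under Protocol 7.4.3.1.1 disease progression "should not be captured as an AE or SAE, unless its outcome is death". A death from progression on day 60 is therefore a fatal treatment-emergent event in 4b and is not counted in 4a. All-cause serious, grade 3 or higher and fatal rows are the most exposed. Crossover widens the gap: under Protocol 3.1.6 it may start within 2 months of the last derazantinib dose, so censoring at crossover can end a 4a patient's window before day 28.

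**Working it through.** **Stated figures.** The documents give no figure for an AE comparison. The only calculation stated for these cohorts is the two-stage response design (Protocol 8.1.3, SAP 6.1.6.4): continue with 2 or more responses in 16, reject with 7 or more in 50. Summing P(X1 = x) × P(Bin(34, p) ≥ 7 − x) over x = 2 to 16 gives 0.0448 at p = 0.07 and 0.8027 at p = 0.20. Both match the plan, and this point does not touch them.

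**Windows.** 90 − 28 = 62 extra days in 4b, and 90/28 = 3.2 times the post-treatment window.

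**Direction.** Crude incidence counts patients with at least one event. Extending the window can add such patients and can never remove one. If the true hazards are equal, 4b can only show the same incidence as 4a or a higher one.

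**Illustration of size.** Time on treatment, AE incidence and post-treatment hazard are not in the documents, so all three are assumptions. Let T be days on treatment (63, 126 or 189, that is 3, 6 or 9 cycles of 21 days) and f the post-treatment hazard as a fraction of the on-treatment hazard, both the same in each cohort. If the incidence in 4a is p, then

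incidence in 4b = 1 − (1 − p)^[(T + 90f)/(T + 28f)].

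Worked case, p = 0.30, T = 63, f = 1: the exponent is 153/91 = 1.681, and 1 − 0.70^1.681 = 0.451, an excess of 15.1 points with no true difference.

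| f | T (days) | 4b when 4a = 30% | Excess (points) | Excess when 4a = 10% (points) |
|---|---|---|---|---|
| 1 | 63 | 45.1% | 15.1 | 6.2 |
| 1 | 126 | 39.4% | 9.4 | 3.7 |
| 1 | 189 | 36.8% | 6.8 | 2.7 |
| 0.25 | 63 | 35.3% | 5.3 | 2.1 |
| 0.25 | 126 | 32.9% | 2.9 | 1.1 |
| 0.10 | 63 | 32.3% | 2.3 | 0.9 |
| 0.10 | 126 | 31.2% | 1.2 | 0.5 |
| 0 | any | 30.0% | 0 | 0 |

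**With a common cut-off.** At 28 days in both cohorts the exponent is (T + 28f)/(T + 28f) = 1, so the excess due to the window is 0 for every T and f.

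**Which common cut-off is possible.** After the last safety visit, Protocol 7.4.4 asks only for drug-related SAEs and AESIs, and "these events should not be captured in the eCRF system". Events in 4a after day 28 are therefore not in the eCRF data, and a 90-day window cannot be built for 4a. Day 28 is the latest cut-off common to both.

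**The case against.** The strongest reply is that no safety comparison is really planned. The cohorts are labelled non-comparative, no AE test is done, and SAP 6.4 specifies no between-cohort difference, interval or p-value. The phrase in SAP 5.1 sits in a population definition with no analysis attached. This stands in part: no error rate is at stake, and the effect is on how descriptive columns are read. It does not remove the point, because both documents name a primary safety comparison and write a 4a-specific censoring rule for it.

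The size may also be small. A constant hazard treats time off drug like time on drug. At 10 to 25% of the on-treatment hazard the excess is 1.2 to 5.3 points, or 0.6 to 2.7 patients in 50, against a standard error for a difference at 30% of √(2 × 0.30 × 0.70/50), about 9 points. This also stands. The excess is systematic, however, and sampling error is not.

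Some rows are largely protected. Rows for related events filter out much of what progression and later therapy cause, although a missing relationship counts as related. DLT, dose-modification and discontinuation rows hardly depend on time after treatment. By-patient listings with study days would let a reader rebuild a day-28 view by hand.

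The 90-day period has a purpose. Protocol 1.4.3.2 gives atezolizumab a half-life of about 3 weeks, and immune-related events are of special interest. A reader might infer that 90-day collection is itself an error, or that every cohort should be cut at 28 days. The documents support neither. Substudy 3 is a single combination arm with no such comparison to protect, and truncating its tables would only move late immune-related events out of view.

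Finally, if Protocol 3.1.5 were the operative rule, both cohorts would have a 90-day visit. The more specific places (Protocol 4.5.1, 5.2.2.9 and 7.4.3, and SAP Table 1 footnote 3) say otherwise.

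**Conclusion.** The point holds as a matter of descriptive reporting. The unequal windows are documented, nothing in SAP 6.4.1 corrects for them, and their effect on crude incidence can run only against the combination. The illustrated excess at 30% incidence in 4a is about 7 to 15 points under a constant hazard and about 1 to 5 points with a post-treatment hazard at 10 to 25% of the on-treatment level. It is zero only if no first events occur in the extra days. These figures rest on assumed treatment durations, incidence and hazards, equal in both cohorts.

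A reader might go further and infer that a planned inferential comparison is biased, or that the fatal-event columns will differ by some known multiple. The documents do not support either: no AE test or between-cohort estimate is specified, and no post-treatment hazard or survival is given from which a size could be calculated. This is a worthwhile but minor improvement.

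**What to change.** In SAP 6.4.1:

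- Keep the existing treatment-emergent definition and the 90-day reporting for atezolizumab-treated patients.
- State that the 4a-versus-4b safety comparison uses events with onset from first dose to 28 days after last dose in both cohorts, with 4a patients censored at crossover as already written.
- Show Cohort 4b events with onset on days 29 to 90 separately.
- Leave the Substudy 3 tables unchanged.

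In the protocol, Section 3.1.5 must be reconciled with 5.2.2.8, 5.2.2.9 and 7.4.3 on which patients have the 90-day visit.

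The cost is one derivation flag and one extra set of tables. AE start dates are already collected, so no new data are needed. Late immune-related events drop out of the comparative table and are read from the existing 90-day tables. The common cut-off does not deal with 4a patients who cross over before day 28. A footnote giving their number would let readers judge what imbalance remains.
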